All tumor biopsy tissue will be submitted in formalin-fixed paraffin-embedded (FFPE) format to the Mayo Clinic where biomarker specimen processing will be centralized. Once the quality of the specimen is verified by expert hematopathologist, ten 4 micron unstained slides will be forwarded to Mosaic Laboratories (Lake Forest, CA) for CD27 IHC assay (integrated biomarker). The remaining tissue block or slides will be used to generate specimens for exploratory biomarker studies including (1) additional unstained slides for IHC evaluation of intra-tumoral immune cells, (2) extraction of tumor DNA for whole-exome sequencing, (3) evaluation of 9p24.1 locus by FISH and (4) mass cytometry analysis of intra-tumoral immune cells all of which will be performed centrally at Mayo Clinic.

Serial collection of peripheral blood is also mandatory for patients participating in this study. Peripheral blood will be collected at baseline and every 14 days (prior to administration of study drugs) for the first 12 weeks on study. Submission of peripheral blood obtained at the time of disease progression is optional. Peripheral blood will be used to generate serum for cytokine profiling, isolation of peripheral blood mononuclear

cells for immunophenotyping, immunogenicity assays and pharmacokinetic studies.

Any surplus of tissue, DNA, cells or serum will be banked at Mayo Clinic for additional studies for the patients who provide additional consent for tissue banking. If consent for banking was not provided by the patient, the remaining blocks or slides will be returned to the original institution after minimum specimens are generated. Surplus of blood, plasma, serum, DNA and cells will be discarded once the minimum specimens are generated if the patient did not provide consent for banking of specimens.

Integrated Correlative Study

Correlative Study	Optional or Mandatory	Required Specimen	Collection Timepoints
	Mandatory	FFPE blocks (preferred) or 3 unstained glass slides with 4-micron-thick sections from FFPE blocks	For all patients: Baseline (Within 60 days of registration)
Quantification/ Characterization of CD27+ cells by IHC	Mandatory	FFPE blocks (preferred) or 3 unstained glass slides with 4-micron-thick sections from FFPE	For patients who cross over from Group 1 to Group 2 only: At the time of progression

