- Methodology: The integrated biomarker (CD27 IHC) assay will be performed on 9.2.1.3 formalin-fixed paraffin-embedded (FFPE) tissue. Biopsies should be obtained under radiologic or other guidance, as appropriate, per institutional procedures. Tissues should be placed in preservative no later than 30 minutes following removal from the body (ideally with 5-10 minutes). If tissue is obtained via core biopsy, a minimum of 3 and up to 6 cores are requested; however, less than the goal amount of tissue is acceptable, and should be based upon the clinical judgment of the clinician performing the procedure. Based upon prior studies, it is feasible for up to 6 to 8 core biopsies to be obtained depending on the site being sampled, the size of the mass, and the safety of the procedure. Specimens should then be fixed using 10% Neutral Buffered formalin for 20 ± -4 hours and then processed into FFPEs. If fixed specimens cannot be processed into FFPE within the period specified above, transfer the specimen to a container of 70% histology-grade alcohol where the specimen can be stable for up to 2 weeks. If the site cannot process tissue into FFPE, then ship specimens in 70% alcohol. Tissue blocks should be ideally released for the biomarker study. In the event this is not possible, serial 4 µm sections should be obtained from each core and mounted on positively-charged unstained glass slides. A total of 3 slides created from biopsy obtained at the time of registration should be forwarded from the Predolin Biobank to Mosaic Laboratories. A repeat biopsy is mandatory for patients who wish to cross-over from Group 1 to Group 2 in the event of progression. Three additional slides obtained at the time of progression should be forwarded from the Predolin Biobank to Mosaic Laboratories for these patients. Additional glass slides will be created for exploratory correlative studies as specified on section 9.1 (Specimen Requirements for Correlative Studies).

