We will stain a minimum of 3 x 10^6 cells per specimen and acquire a minimum of 1 x 10^6 events on the CyTOF. We will initially perform high-level manual gating to exclude dead or apoptotic cells, debris, beads and doublets. Additional multiparametric analysis will be done using platforms such as Spanning-tree Progression Analysis of Density-normalized Events (SPADE) and visualization of unbiased clustering of events using the t-SNE (t-Distributed Stochastic Neighbor Embedding) algorithm or viSNE.

- 9.3.2 Identification/Characterization of Intratumoral Immune Cells by Immunohistochemistry (IHC) and CyTOF
- 9.3.2.1 Collection of Specimen(s): FFPE tumor tissue

9.3.2.2 Handling and Shipping of Specimens(s): FFPE tumor block(s) are preferred. Alternatively, a minimum of 13 unstained glass slides with 4-micron thick sections from FFPE per collection timepoint are acceptable. Please include a copy of the deidentified surgical pathology report, as well as study, site and patient study numbers. All FFPE specimens for correlative studies may be shipped together.

Shipping Procedure:

- 1. Place the block or slides in small zip-lock bag and seal.
- 2. Insert the bag containing the block or the slides in a bubble wrap bag.
- 3. Place wrapped samples inside the largest compartment of specimen biohazard bag and seal.
- 4. Insert a copy of the de-identified surgical pathology report in the outer pocket of the specimen biohazard bag.
- 5. Include a refrigerated cold pack (not frozen) if shipping in the summer months.
- 6. Place the specimen biohazard bag into the box and close.
- 7. Complete the transport documents and place into waybill pouch; affix to box.
- 8. Ship package to Mayo Clinic at the address below.
- 9. Please send email on the day of the shipment.

Please send FFPE tissue to:

Predolin Biobank Attn: [name] Mayo Clinic [name]

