9.3.2.3 Methodology: Serial 4-µm paraffin-embedded sections will be used for IHC. The tissue will be deparaffinized with three changes of xylene and cleared through graded series of ethanol. Endogenous peroxidase will be quenched by incubation in 50% methanol/H2O2 and after rinsing with tap water; all sections will be pretreated for 30 minutes with 50 mmol/L EDTA using a steamer and cooled for additional 5 minutes. All staining will be done automatically on DAKO Autostainer using the following antibodies to CD11c (Leica Microsystems 5D11), CD14 (Cell Marque EPR 3653), CD163 (DAKO 1F8), CD68 (DAKO PG-M1), CXCL13 (R&D Systems 53610), FOXP3 (Abcam 236AE/7), CD3 (R&D Systems), PD-L1 (405.9A11), PD-L2 (366C.9E5), CD8a (Dako M7103) and PD-1 (Abcam NAT). The sections will be viewed with an Olympus BXFA51 microscope and pictures taken with an Olympus DP71 camera. Stained slides will be scored by expert hematopathologist. Internal control (reactive lymph node, tonsil) will be used to verify staining quality. Analysis of intra-tumoral immune cell subsets by IHC will be largely exploratory and reported descriptively.

For CyTOF analysis of intra-tumoral immune cells, we will perform multiparametric staining of single-cell suspensions obtained from FFPE blocks using the FFPE-

DISSECT (disaggregation for intracellular signaling in single epithelial cells from tissue) method. Single cells will be stained with the same 34-parameter surface protein panel (Appendix F). Nucleated cellular events will be identified using a DNA intercalator conjugated to natural abundance iridium (¹⁹¹Ir and ¹⁹³Ir). Cisplatin (¹⁹⁵Pt) will be used for dead-live cell discrimination and calibration beads containing natural abundance cerium (^{140/142}Ce), europium (^{151/153}Eu), holmium (¹⁶⁵Ho), and lutetium (^{175/176}Lu) will be used for normalization of acquired data. Our panel will be constructed using commercially available metal-conjugated antibodies (Fluidigm Corporation) and stained cells will acquired on the CyTOF2 (Fluidigm Corporation).

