We will stain a minimum of $3 \ge 10^6$ cells per specimen and acquire a minimum of $1 \ge 10^6$ events on the CyTOF. We will initially perform high-level manual gating to exclude dead or apoptotic cells, debris, beads and doublets. Additional multiparametric analysis will be done using platforms such as Spanning-tree Progression Analysis of Density-normalized Events (SPADE) and visualization of unbiased clustering of events using the t-SNE (t-Distributed Stochastic Neighbor Embedding) algorithm or viSNE.

- 9.3.3 Evaluation of Genetic Alterations in Chromosome 9p24.1 by FISH
- 9.3.3.1 Collection of Specimen(s): FFPE tumor tissue
- 9.3.3.2 Handling and Shipping of Specimens(s): FFPE tumor blocks are preferred. Alternatively, a minimum of 13 unstained glass slides with 4-micron thick sections from FFPE per collection timepoint are acceptable. Please include a copy of the deidentified surgical pathology report, as well as study, site and patient study numbers. All FFPE tissue for correlative studies may be shipped together.

Shipping Procedure:

- 1. Place the block or slides in small zip-lock bag and seal.
- 2. Insert the bag containing the block or the slides in a bubble wrap bag.
- 3. Place wrapped samples inside the largest compartment of specimen biohazard bag and seal.
- 4. Insert a copy of the de-identified surgical pathology report in the outer pocket of the specimen biohazard bag.
- 5. Include a refrigerated cold pack (not frozen) if shipping in the summer months.
- 6. Place the specimen biohazard bag into the box and close.
- 7. Complete the transport documents and place into waybill pouch; affix to box.
- 8. Ship package to Mayo Clinic at the address below.
- 9. Please send email on the day of the shipment.

Please send FFPE tissue to:

Predolin Biobank Attn: [name] Mayo Clinic [name]

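### The intratumoral CyTOF plan applies a live/dead stain and a dead-cell exclusion to formalin-fixed tissue, where viability cannot define which events are kept

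*Combined protocol and SAP*

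**What the plan says.** Section 9.1 sets the tumour specimen format: "All tumor biopsy tissue will be submitted in formalin-fixed paraffin-embedded (FFPE) format to the Mayo Clinic where biomarker specimen processing will be centralized". Section 9.2.1.3 describes the preparation: "Specimens should then be fixed using 10% Neutral Buffered formalin". Its only fallback is also a preservative: "If the site cannot process tissue into FFPE, then ship specimens in 70% alcohol". Section 9.3.2.1, which covers intratumoral immune cells, gives the specimen as "Collection of Specimen(s): FFPE tumor tissue".

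Section 9.3.2.3 then sets out the tumour CyTOF assay. The cells come from the blocks: "For CyTOF analysis of intra-tumoral immune cells, we will perform multiparametric staining of single-cell suspensions obtained from FFPE blocks". An iridium DNA intercalator identifies nucleated events. Cisplatin "will be used for dead-live cell discrimination and calibration beads containing natural abundance cerium" and other metals used for normalisation. The first analysis step is: "We will initially perform high-level manual gating to exclude dead or apoptotic cells, debris, beads and doublets".

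The stain and gating sentences also appear in Section 9.3.1.3 for peripheral blood. There the cells are frozen in medium containing 10% dimethyl sulfoxide and are described as live when stained. Section 2.4.2.1 lists both specimen types and then calls cisplatin a viability marker without distinguishing them.

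**The concern.** A viability gate presupposes that some cells are alive when they are stained. That is reasonable for cryopreserved blood cells. It is not possible for cells released from a block that has been through formalin and paraffin. The tumour paragraph appears to carry over the blood assay's stain and gate with a changed cell source. This is more than a missing threshold, because no threshold on this stain would make the stated criterion apply to the stated specimen.

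At stake is the interpretability of one exploratory readout. Section 13.5 plans to describe intratumoral subsets by IHC and CyTOF and to relate such measures to clinical outcome. This includes before-and-after comparisons, responders against non-responders, and models for PFS and OS. Section 13.5 expresses the blood subsets as a percentage of the parent population and describes the tumour assessment as similar. The first gate therefore fixes the pool of events behind every tumour subset fraction.

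**Working it through.** The plan gives no figure to reproduce. The check follows the specimen from collection to gating and compares the two CyTOF assays.

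| Step | Blood (9.3.1.3) | Tumour (9.1, 9.2.1.3, 9.3.2.3) |
|---|---|---|
| Preservation | Frozen in 10% dimethyl sulfoxide medium | Formalin, then paraffin; 70% alcohol as fallback |
| State when stained | Described as live | Released from an FFPE block, so already fixed |
| Viability stain | Cisplatin | Cisplatin |
| First gate | Excludes dead or apoptotic cells, debris, beads, doublets | Same sentence |
| Separate rule for fixed cells | Not needed | None found |

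**1. Is there a route by which viable tumour cells reach the stain?** No. Section 9.1 sends all tumour tissue as FFPE, and the specimen tables there list only FFPE blocks or FFPE slides. Section 9.2.1.3 puts tissue into preservative within 30 minutes of removal. No fresh or viably frozen tumour is collected.

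**2. Could the gate refer to cells that were dead before fixation?** That would need a viability label applied before fixation. None is described, and in 9.3.2.3 staining follows disaggregation of the block.

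**3. What does the gate keep if read literally?** Events kept = events acquired × viable fraction. Section 9.3.2.3 requires at least 1 × 10⁶ acquired events per specimen. With a viable fraction of 0, 1 × 10⁶ × 0 = 0. This only puts the logic in numbers. It does not predict what the instrument would show.

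**4. What if an operator keeps some events?** The gating is manual and no cut-off is given. Whatever cisplatin signal separates kept from discarded events, it is not live against dead. The documents do not say what it would reflect.

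**5. How many specimens are involved?** The upper bound is the mandatory baseline biopsy in at most 106 patients (Section 13.2.1), plus the mandatory biopsy in Group 1 patients who cross over, plus optional off-study biopsies. The true number is smaller or unknown. Sites may send slides instead of blocks, with a minimum of 13 per timepoint. Section 9.1 allots these as 3 (CD27) + 7 (intratumoral IHC and CyTOF) + 1 (FISH) + 2 (exome sequencing) = 13. The CyTOF text takes suspensions from blocks and asks for at least 3 × 10⁶ stained cells. Nothing shows that slide-only patients or small cores can supply that.

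**The case against.** The strongest reply is that this is bench wording carried over from one assay to another, and that a competent laboratory would work around it. The gate is manual and has no fixed cut-off. Its debris, bead and doublet exclusions remain valid, and the iridium intercalator already identifies nucleated events. A laboratory that found cisplatin uninformative could gate on intact nucleated singlets with steps already in the plan. The named FFPE disaggregation method may also have its own gating practice, which the documents do not describe. All of this is fair, and it makes complete loss of data unlikely in practice. It does not rescue the text: the laboratory would be departing from the written rule by an unrecorded choice, which could differ between specimens.

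Several stronger readings are tempting, and the documents do not support them:

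- *All tumour CyTOF data will be lost, or the kept cells will reflect fixation and permeability.* Both depend on how cisplatin labels FFPE-derived cells, which the documents do not state.
- *Associations with response, PFS or OS will be biased.* No size or direction can be derived. Section 9.2.1.3 standardises time to fixative and fixation time, which limits one source of variation. Baseline biopsies are taken before registration, so gating error there has no stated route to differ by arm.
- *Exploratory objective 1.3.1 fails for tumour tissue.* The objective also names IHC, and 9.3.2.3 provides an intratumoral IHC panel with no viability gate.
- *106 patients are affected.* That is only a ceiling for the baseline biopsy, as shown in the working.

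**Conclusion.** The point holds as a defect in a stated assay rule: a viability stain and a dead/apoptotic exclusion are prescribed for cells that were all fixed before staining. Read literally, the rule leaves no analysable events. Applied with a hand-set cut-off, it keeps a subset that viability does not define.

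The scope is narrow. Only intratumoral CyTOF is touched, in however many specimens yield enough cells. Blood CyTOF, intratumoral IHC, the integrated CD27 IHC marker and the primary response comparison stand as they are, and no decision rule in Section 13.1.3 uses the tumour CyTOF result. The work is labelled exploratory and largely descriptive, so this is a minor correction.

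The conclusion assumes that cells taken through formalin and paraffin are not viable, which follows from the preparation the protocol describes. It also assumes that no laboratory procedure outside these documents already replaces the gate.

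**What to change.** In Section 9.3.2.3, for FFPE-derived suspensions:

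- Remove cisplatin as a live/dead stain.
- Remove dead or apoptotic cells from the list of exclusions.
- Define analysable events as intact nucleated singlets by the iridium DNA intercalator, with debris, bead and doublet exclusion applied identically to all tumour specimens.

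In Section 2.4.2.1, state that cisplatin viability gating applies to blood mononuclear cells only. Without this edit the background section would still contradict the revised method. Section 9.3.1.3 (blood) needs no change.

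The cost is about two sentences in 9.3.2.3 and one in 2.4.2.1, with no extra tissue, samples or procedures. The change should be made before tumour specimens are gated, so that the definition does not depend on the data.

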10. STUDY CALENDAR

Baseline evaluations are to be conducted within 14 days prior to registration unless stated otherwise. Biopsy for FFPE may be obtained within 60 days prior to registration. Scans and x-rays must be done \leq 4 weeks prior to the start of therapy. In the event that the patient's condition is deteriorating, laboratory evaluations should be repeated within 48 hours prior to initiation of the next cycle of therapy. The frequency of routine evaluations (physical, vital signs, routine laboratory tests) changes from every 2 weeks to every 4 weeks after 4 months to accommodate the change in administration schedule of nivolumab.

		Сус	Cycle 1 Cycle 2		ele 2	Cycle 3		Cycle 4		Cycles 5 and beyond*		
	Pre- Study	Week 1	Week 3	Week 5	Week 7	Week 9	Week 11	Week 13	Week 15	Week 17 and beyond	Off Study ^d	
CDX-1127 (Varlilumab)		V		V		V		V		V		
Nivolumab		N	N	N	N	Ν	N	Ν	Ν	Ν		
Informed consent	Х											
Demographics	Х											
Medical history	X											
Concurrent meds	X	X	Х	Х	Х	Х	Х	Х	Х	Х	Х	
Physical exam	Х	Х	Х	Х	Х	Х	Х	Х	Х	Х	Х	
Vital signs	Х	Х	Х	Х	Х	Х	Х	Х	Х	Х	Х	
Height	Х											
Weight	Х	Х	Х	Х	Х	Х	Х	Х	Х	Х	Х	
Oxygen saturation	Х	Х	Х	Х	Х	Х	Х	Х	Х	Х	Х	
Performance	Х	Х	Х	Х	Х	Х	Х	Х	Х	Х	Х	

status											
Lab tests ^a	X	Х	Х	Х	Х	X	X	Х	Х	X	Х
Evaluation of Cardiac Function X											
Adverse event evaluationXXXXXXX						Х	Х				
Radiologic evaluation	X		fr	Radiologic measurements should be performed every 12 weeks from C1D1 (+/- 3 days). Documentation (radiologic) should must be provided for patients removed from study for progressive disease							ould must
B-HCG	X ^b	X ^g									
FFPE for Correlatives X ^c						Xc					
Blood for correlatives ^f	X	Х	Х	Х	Х	Х	Х				
N: Niv mg a: Lal adr pho cre SG Lal	volumab every 4 o tests to ninistrat osphatase atinine, : PT [AL]	: All pa weeks to be perf ion inclue, total b fasting g [], sodiu	tients: hereaft ormed ude cor bilirubin glucose um, am	240 mg er at basel nplete b n, bicarl , LDH, ylase, li	ine and plood co bonate, phosph pase, T	2 weeks within ount (CH BUN/u orus, po SH (with	$5 \pm 2 \text{ day}$ 72 hour 3C) with rea, cal- ptassium th reflex	ys for 4 rs prior h differ cium, m h, total j kive Fre	months to each ential; a nagnesiu protein, ee T4 ar	eks ± 2 day s followed l study drug llbumin, all um, chlorid SGOT [AS of Free T3) o receive stu	by 480 kaline e, ST],

b: Serum or urine pregnancy test for females of childbearing potential.

well.

c.	A pre-study biopsy is mandatory for all groups and must be obtained within 60 days prior to registration. For Group 1 patients who elect to cross over to Group 2, a biopsy is mandatory at that time. An off-study biopsy is optional for all groups.
d:	Off-study evaluation to be performed 30 days (+/- 14 days) after the last dose of study drug. Patients are followed for at least 100 days for AE assessment.
e:	As clinically indicated, perform an evaluation of cardiac function including ECG and echocardiogram for any patients with a history of CHF or at risk because of underlying cardiovascular disease or exposure to cardiotoxic drugs. Also perform an evaluation for patients with evidence of CHF, MI, cardiomyopathy, or myositis including lab tests and cardiology consultations including ECG, echocardiogram, CPK and troponin.
f:	Blood draw for correlative studies will be obtained at baseline (within 14 days prior to start of protocol therapy) and within 72 hours prior to the administration of any of the study drugs on dosing days. These blood draws may be performed at the same occasion as other laboratory tests obtained for the purpose of clinical monitoring of the patient. Patients who cross-over from Group 1 to Group 2 will need 4 additional blood draws pre-dose prior to their first 4 infusions of CDX-1127 (varlilumab) for immunogenicity and PK studies.
g:	A serum or urine pregnancy test is required within 24 hours of starting study treatment. If the pre-study assessment was performed within 24 hours prior to start of study treatment, a pregnancy test does not need to be repeated.
*:	Starting with Cycle 5 (Week 17), the dosage and administration schedule of nivolumab is changed to 480 mg every 4 weeks. The dosage and administration schedule of CDX-1127 (varlilumab) remains unchanged. Once the schedule of administration of nivolumab changes, the frequency of routine evaluations also changes accordingly to every 4 weeks as

11. MEASUREMENT OF EFFECT

11.1 Antitumor Effect – Hematological Tumors

11.1.1 Definitions

Evaluable for toxicity: All patients will be evaluable for toxicity from the time of their first treatment with CDX-1127 (varlilumab) and/or nivolumab

Evaluable for objective response: All patients fulfilling eligibility criteria that have signed a consent form and have begun treatment will be considered evaluable for response. These patients will have their response classified according to the definitions stated below. (Note: Patients who exhibit objective disease progression prior to the end of cycle 1 will also be considered evaluable.)

11.1.2 Response Criteria

Patients will be evaluated for efficacy based on the lymphoma response to immunomodulatory therapy criteria or LYRIC (Cheson *et al.*, 2016).

11.1.3 Schedule of Evaluations

PET/CT scans are required at baseline for all patients. Repeat PET-CT scans should be obtained every 12 weeks unless otherwise clinically indicated.

Definitions for clinical response for patients with lymphoma are based on the lymphoma response to immunomodulatory therapy criteria or LYRIC (Cheson *et al.*, 2016). Lymph node measurements should be taken from the CT portion of the PET/CT, or other dedicated CT scans where applicable. Measurement of lymphadenopathy for purposes of assessing for PR will be determined by adding the sum of the products of the maximal perpendicular diameters of measured lesions (SPD). The perpendicular diameter of a single node is sufficient to evaluate for PD (see Table 11.1.4). Measurable extranodal disease should be assessed in a manner similar to that for nodal disease. For these recommendations, the spleen is considered nodal disease. Disease that is only assessable (*e.g.*, pleural effusions, bone lesions) will be recorded as present or absent only, unless, while an abnormality is still noted by imaging studies or physical examination, it is found to be histologically and pathologically negative.

For response assessment, PET-CT is preferred for staging of FDG-avid lymphomas and CT scan is preferred in the other lymphomas

Progressive disease is based on either PET-CT based (PMD) or CT based (PD) response criteria. Definition of progressive disease according to LYRIC is same as the Lugano classification except that a new category of indeterminate response (IR) is added. Patients whose disease fall in the IR category may continue treatment for additional 12 weeks if the patient remains clinically stable as judged by the treating physician. A repeat imaging

study in 12 weeks (or earlier if clinically indicated) is mandatory to confirm or refute disease progression. PET confirmation of progressive disease is per physician discretion.

11.1.4 Lymphoma Response to Immunomodulatory Therapy Criteria [LYRIC] (adapted from Cheson *et al.*, 2016)

	PET-CT Based Response	CT-Based Response
Complete Response (CR)	Complete metabolic response (CMR)	Complete radiologic response (CR) (all of the following)
Lymph nodes and extra lymphatic sites	Score 1, 2, or 3 ^a with or without a residual mass on 5PS [†] It is recognized that in Waldeyer's ring or extranodal sites with high physiologic uptake or with activation within spleen or marrow (e.g. , with chemotherapy or myeloid colony-stimulating factors), uptake may be greater than normal mediastinum and/or liver. In this circumstance, complete metabolic response may be inferred if uptake at sites of initial involvement is no greater than surrounding normal tissue even if the tissue has high physiologic uptake	Target nodes/nodal masses must regress to ≤ 1.5 cm in LDi No extra lymphatic sites of disease
Non-measured lesion	Not applicable	Absent
Organ enlargement	Not applicable	Regress to normal
New lesions	None	None
Bone marrow	No evidence of FDG-avid disease in marrow	Normal by morphology; if indeterminate, IHC negative
Partial Response (PR)	Partial metabolic response (PMR)	Partial remission (PR) (all of the following)
Lymph nodes and extra lymphatic sites	Score 4 or 5 [†] with reduced uptake compared with baseline and residual mass(es) of any size At interim, these findings suggest responding disease At end of treatment, these findings indicate residual disease	\geq 50% decrease in SPD of up to 6 target measurable nodes and extranodal sites When a lesion is too small to measure on CT, assign 5 mm X 5 mm as the default value When no longer visible, 0 X 0 mm For a node > 5 mm X 5 mm, but

	PET-CT Based Response	CT-Based Response
		smaller than normal, use actual measurement for calculation
Non-measured lesions	Not applicable	Absent/normal, regressed, but no increase
Organ enlargement	Not applicable	Spleen must have regressed by > 50% in length beyond normal
New lesions Bone marrow	None Residual uptake higher than uptake in normal marrow but reduced compared with baseline (diffuse uptake compatible with reactive changes from chemotherapy allowed). If there are persistent focal changes in the marrow in the context of a nodal response, consideration should be given to further evaluation with MRI or biopsy or an interval scan	None Not Applicable
No Response or Stable Disease	No metabolic response (NMR)	Stable disease (SD)
Target nodes/nodal masses, extranodal lesions	Score 4 or 5 with no significant change in FDG uptake from baseline at interim or end of treatment	< 50% decrease from baseline in SPD of up to 6 dominant, measurable nodes and extranodal sites; no criteria for progressive disease are met
Non-measured lesions	Not applicable	No increase consistent with progression
Organ enlargement	Not applicable	No increase consistent with progression
New lesions Bone marrow	None No change from baseline	None Not Applicable
Indeterminate Response (IR)		
IR(1) ^b		\geq 50% increase in SPD of up to 6 measurable lesions in first 12 weeks without clinical deterioration. Note: The measurements from the first IR (1) time point becomes the reference against which future assessment will be compared. An increase of \geq 10% (in addition to an increase of \geq 5 mm in either dimension of \geq 1 lesion for lesions \leq

	PET-CT Based Response	CT-Based Response
		2cm and 10 mm for lesions > 2 cm) constitutes PD
		< 50% increase in SPD of up to 6 measurable lesions with: a. new lesion(s), or b. ≥ 50% increase in PPD of a lesion or set of lesions at any time during treatment.
IR(2)		Note: The new or growing lesion(s) (unless biopsy proven to be benign) should be added to the target lesion(s), up to a total of no more than 6 total lesions. In future assessments, if the SPD of the newly defined set of target lesions has increased $\geq 50\%$ from their nadir value (which may precede the IR time point), the patient should be considered to have PD.
IR(3)	Increase in FDG uptake of 1 or more lesion(s) without a concomitant increase in lesion size or number. Note: Because inflammatory responses may result in an increase in the standardized uptake value of a lesion, the patient will not be considered to have PD unless there is evidence of PD by an increase in lesion size or the development of new lesions, as noted below.	
D	*** Excludes patients who meet criteria	for Indeterminate Response (IR) ***
Progressive disease (PD)	Progressive metabolic disease (PMD)	Progressive disease (PD) requires at least 1 of the following
Individual target nodes/nodal masses Extranodal lesions	Score 4 or 5 with an increase in intensity of uptake from baseline and/or New FDG-avid foci consistent with lymphoma at interim or end-of-treatment assessment	An individual node/lesion must be abnormal with: LDi > 1.5 cm and Increase by ≥ 50% from PPD nadir and An increase in LDi or SDi from nadir 0.5 cm for lesions ≤2 cm 1.0 cm for lesions >2 cm In the setting of splenomegaly, the splenic length must increase by >

	PET-CT Based Response	CT-Based Response
		50% of the extent of its prior increase beyond baseline (e.g. , a 15 cm spleen must increase to >16 cm). If no prior splenomegaly, must increase by at least 2 cm from baseline New or recurrent splenomegaly
Non-measured lesions	None	New or clear progression of preexisting non-measured lesions
New lesions	New FDG-avid foci consistent with lymphoma rather than another etiology (e.g. , infection, inflammation). If uncertain regarding etiology of new lesions, biopsy or interval scan may be considered	Regrowth of previously resolved lesions A new node >1.5 cm in any axis A new extranodal site >1.0 cm in any axis; if <1.0 cm in any axis, its presence must be unequivocal and must be attributable to lymphoma Assessable disease of any size unequivocally attributable to lymphoma
Bone marrow	New or recurrent FDG-avid foci	New or recurrent involvement

Abbreviations: 5PS, 5-point scale; CT, computed tomography; FDG, fluorodeoxyglucose; IHC, immunohistochemistry; LDi, longest transverse diameter of a lesion; MRI, magnetic resonance imaging; PET, positron emission tomography; PPD, cross product of the LDi and perpendicular diameter; SDi, shortest axis perpendicular to the LDi; SPD, sum of the product of the perpendicular diameters for multiple lesions.

a. A score of 3 in many patients indicates a good prognosis with standard treatment, especially if at the time of an interim scan. However, in trials involving PET where de-escalation is investigated, it may be preferable to consider a score of 3 as inadequate response (to avoid under treatment). Measured dominant lesions: Up to six of the largest dominant nodes, nodal masses, and extranodal lesions selected to be clearly measurable in two diameters. Nodes should preferably be from disparate regions of the body and should include, where applicable, mediastinal and retroperitoneal areas. Non-nodal lesions include those in solid organs (e.g., liver, spleen, kidneys, and lungs), GI involvement, cutaneous lesions, or those noted on palpation. Non-measured lesions: Any disease not selected as measured, dominant disease and truly assessable disease should be considered not measured. These sites include any nodes, nodal masses, and extranodal sites not selected as dominant or measurable or that do not meet the requirements for measurability but are still considered abnormal, as well as truly assessable disease, which is any site of suspected disease that would be difficult to follow quantitatively with measurement, including pleural effusions, ascites, bone lesions, leptomeningeal disease, abdominal masses, and other lesions that cannot be confirmed and followed by imaging. In Waldeyer's ring or in extranodal sites (e.g., GI tract, liver, bone marrow), FDG uptake may be greater than in the mediastinum with complete metabolic response, but should be no higher than surrounding normal physiologic uptake (*e.g.*, with marrow activation as a result of chemotherapy

	PET-CT Based Response		CT-Based Response				
	or myeloid g	rowth factors).					
 † PET Deauville 5PS: 1, no uptake above background; 2, uptake ≤ mediastinum; 3, uptake > mediastinum but ≤ liver; 4, uptake moderately > liver; 5, uptake markedly higher than liver and/or new lesions; X, new areas of uptake unlikely to be related to lymphoma. 							
	-	s assessed as having IR and then "true" PD at objective response between IR and PD), the II					

intervening objective response between IR and PD), the IR assessment should subsequently be corrected to PD for reporting purposes to the date of the prior designation of IR. We recognize that these lesions may remain stable during the time of observation, but, even if this is the case, the initial designation of IR should be changed to PD.

